9.3. SUBJECT DISPOSITION, DEMOGRAPHIC AND BACKGROUND CHARACTERISTICS

Subject disposition, demographic characteristics, and background variables will be summarized by treatment group.

9.4. ANALYSIS OF EFFICACY

To assess whether AXR-270 Cream is more effective than Vehicle, exploratory efficacy will be performed. The unit of analysis for ophthalmic efficacy measures depends on the measure itself. Some endpoints will be analyzed by eye whereas others will be analyzed by study eyelid, where study eye/eyelid are defined in Section 4.3.

The following parameters will be assessed by eyelid:

- Vascularity of eyelid margin
- Total MGD Score
- LGS grade

The following parameters will be assessed by eye:

- VAS for Eye Discomfort (one score for both eyes)
- VAS for Eye Dryness (one score for both eyes)
- TBUT
- Total and Individual FCS score
- OSDI (subject level)
- Modified BLISS (one score for both eyes)
- Bulbar Conjunctival Hyperemia
- Unanesthetized Schirmer score

VAS scores, Total MGD score, eyelid margin vascularity, LGS grade, conjunctival hyperemia, Schirmer score, TBUT, FCS, and OSDI will be analyzed as continuous data. Analysis will be performed at each timepoint using summary statistics as well as a longitudinal model.

All other parameters will be analyzed as categorical or discrete measures. Frequencies and percentages of each category as well as a shift from baseline (Visit 2/Day 1) to each timepoint will be summarized.

Analyses of all efficacy endpoints will be done using the FAS. Analyses on the study eye/eyelid will be repeated for all non-study eye/eyelids as supportive analyses. Analyses may also be repeated on the PPS.

9.5. ANALYSIS OF SAFETY

Analysis of safety data will be presented for all subjects in the Safety Population. AEs will be coded using Medical Dictionary for Regulatory Activities (MedDRA, most current version) and categorized by system organ class using preferred terms. AEs will be tabulated by treatment group with respect to their Severity and relationship to the IP. Ophthalmoscopy findings will be summarized descriptively. IOP measurements, BCVA, dilated ophthalmoscopy, and slit-lamp biomicroscopy (including external eye exam) will be summarized as safety outcomes.

9.6. SAMPLE SIZE ESTIMATION

As this study is exploratory in nature, no formal sample size calculation was performed.

9.7. LEVEL OF SIGNIFICANCE

P-values will be descriptive in nature.

9.8. PROCEDURE FOR ACCOUNTING FOR MISSING, UNUSED, OR SPURIOUS DATA

Any missing, unused, or spurious data will be noted in the final clinical study report. The data will be analyzed as reported. The last observation carried forward approach will be used to analyze incomplete datasets.

9.9. PROCEDURE FOR REPORTING DEVIATIONS FROM THE STATISTICAL PLAN

Any deviations from the statistical analysis plan will be described and a justification given in the final clinical study report.

10. DIRECT ACCESS TO SOURCE DATA/DOCUMENTS

The Investigator will permit trial-related monitoring, audits, IRB review, and regulatory inspection(s) by providing direct access to source data and documents (such as tests performed as a requirement for participation in the study and other medical records required to confirm information contained in the eCRF such as medical history) to the monitor or appropriate designee.

11. QUALITY CONTROL

The progress of the study will be monitored by on-site, written, e-mail, and telephone communications between personnel at the study center and the Sponsor (or designated monitor). The Investigator will allow AxeroVision, Inc. monitors or designees to inspect all eCRFs; subject records (source documents); signed informed consent forms; HIPAA authorizations; records of IP receipt, storage, and disposition; and regulatory files related to the study.

12. ETHICS

12.1. Institutional Review Board

This protocol and the informed consent form must be approved by an appropriately constituted and qualified IRB and the approvals made available to the Sponsor or designee prior to the start of enrollment into the study. Materials used to recruit subjects will be approved by the appropriate IRB and the approvals made available to the Sponsor or designee prior to their use. In addition, the Investigator's Brochure should be submitted to the IRB. Written IRB approval must adequately identify the protocol and ICF. Copies of all approved materials, all correspondence with the IRB, and written approval from the IRB must be made available to the Sponsor (or designated monitor).

Any modification of study procedures or amendments to the protocol must be approved by the IRB prior to implementation. In the event that a modification or amendment is considered by the Investigator to be immediately necessary to ensure subject safety, the Investigator will promptly notify his or her IRB and the Sponsor.

Investigators will report all SAEs reported at their site to their IRB, as appropriate.

12.2. Informed Consent Requirements

Written informed consent will be obtained from each participant prior to any study-related procedures being performed (prior to or upon Visit 1/Screening). A copy of the signed and dated informed consent document will be given to each subject. The original signed and dated informed consent document must be maintained in the study files at the investigative site and be available for Sponsor or designee review.

Each informed consent will contain Investigator contact information with a telephone number the subject or the subject's authorized representative can call 24 hours a day if they have medical concerns.

13. DATA HANDLING AND RECORDKEEPING

All procedures for the handling and analysis of data will be conducted using GCP and will meet ICH guidelines and FDA regulations for the handling and analysis of data for clinical trials.

13.1. Data Quality Control and Reporting

After data have been entered into the study database, a system of computerized data validation checks will be implemented and applied to the database. Query reports pertaining to data omissions and discrepancies will be forwarded to the clinical Investigator and monitor(s) for resolution. The study database will be updated in accordance with the resolved query reports. All changes to the study database will be documented.

13.2. Records Retention

The study center will retain all records related to the study in accordance with local and ICH GCP guidelines.

14. PUBLICATION POLICY

The institution and Investigators participating in this trial shall have no right to publish or present the results of this study without the prior written consent of the Sponsor.

16. APPENDICES

APPENDIX 1: SCHEDULE OF EVENTS

	Visit 1	Visit 2	Visit 3	Visit 4	Visit 5
Procedures	Day minus 14 (±2 days)	Day 1	Day 8 (±2 days)	Day 15 (±3 days)	Day 22 (±3 days)
	Screening	Randomization	Week 1	Week 2	Week 3
	Equalization Period	Treatment Period			Study Termination
Informed Consent	X				
Inclusion/Exclusion Criteria	X	X			
Randomization Criteria		X			
Demographics, Systemic and Ocular Medical History	X				
Subject-rated Symptom Assessments VAS (Eye Discomfort and Eye Dryness)	X	X	X	X	X
OSDI	X	X	X	X	X
Modified BLISS	X	X	X	X	X
Concomitant Medication Query	X	X	X	X	X
Adverse Event Query		X	X	X	X
UPT	X				X
BCVA	X	X	X	X	X
Slit-lamp Biomicroscopy (including External Eye Exam)	X	X	X	X	X
TBUT	X	X	X	X	X
FCS	X	X	X	X	X
Investigator-rated assessment of signs of MGD: Total MGD Score Eyelid margin vascularity Bulbar conjunctival hyperemia	X	X	X	X	X
LGS ^a	X	X	X	X	X
Unanesthetized Schirmer Test	X	X	X	X	X
IOP	X	X	X	X	X
Dilated Ophthalmoscopy	X				X
Safety Lab Draw		X			X
Dispense Investigational Product for Home Administration		X			
Dispense Daily Dosing Diaries / IP Comfort Assessment Questionnaire		X			
In Clinic Administration of Investigational Product, IP Comfort Assessment Questionnaire and Instruction on Proper Administration ^b		X			
Collect/Review Daily Dosing Diary, IP Comfort Assessment Questionnaire and Investigational Product			X ^c	X	X
Study Termination					X

Key: OSDI=Ocular Surface Disease Index; TBUT=Tear Break up Time; BLISS= BLEpharItIS Symptom; AE=Adverse Event; UPT=Urine Pregnancy Test; IOP=Intraocular Pressure; VAS=Visual Analog Scale; BCVA=Best Corrected Visual Acuity; FCS=Fluorescein Corneal Staining; LGS=Lissamine Green Staining; IP=Investigational Product.

^aOnly to be performed at a subset of sites

^bIncludes dosing video on proper administration of IP

^cIP will not be collected at Visit 3

APPENDIX 2: DATA SAFETY REVIEW COMMITTEE (DSRC)

A description of the function and membership of the masked DSRC will be detailed in a separate charter describing the agreed upon standard operating procedures. The general plan for the review and description of the committee is outlined here:

- A review of safety will be conducted by the DSRC after the last of those 15 subjects has completed Visit 4.
- The DSRC will be minimally comprised of an independent Ophthalmologist and a Statistician who are otherwise not involved in the conduct of the study.
- The DSRC may request the participation of an independent Statistician to assist in the assessment of the safety of the IP and the decision to continue enrolling subjects after the first 15 have been treated and have completed study procedures through Visit 4.
- In order to maintain the integrity of the trial, unless it is absolutely necessary, the safety evaluation should be conducted using masked subject-specific information.
- Upon review of the safety data obtained in the first 15 subjects in Cohort 1, the DSRC will issue a memorandum to AxeroVision, Inc. recommending one of the following:
 1. Continue with the low-dose Cohort 1 and expand study to high-dose Cohort 2 upon completion of enrollment in Cohort 1.
 2. Continue with enrollment in the low-dose Cohort 1 but conduct an additional review of safety information from the next 15 subjects reaching the 2-week mid-point of the study before deciding to recommend escalation to Cohort 2.
 3. Stop study due to safety concerns.
- If, upon the review of the masked safety information, the DSRC requires unmasked information in order to ensure the safeguard of the interests of the study subjects, the unmasked information will be provided per the details outlined in the charter.
- The DSRC will make every effort to arrive to a decision by consensus.

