3.2. DESCRIPTION OF TRIAL DESIGN

Design and Investigational Plan:

This is a multi-center, double-masked, randomized, vehicle-controlled, two cohort study. Subjects will be randomized into either 0.2% AXR-270 Cream (approximately 42 subjects in Cohort 1), 2.0% AXR-270 Cream (approximately 42 subjects in Cohort 2) or Vehicle (approximately 42 subjects) administered in both eyes.

Cohort 1:

Approximately sixty-three (63) subjects with a diagnosis of symptomatic posterior blepharitis associated with MGD meeting all inclusion/exclusion criteria at the Screening visit (Visit 1) will be asked to discontinue their eyelid hygiene regimen and use only Sponsor supplied commercial sterile eyelid wipes between Visit 1 and Visit 2 daily (Equalization Period). Subjects will then be evaluated at Baseline/Randomization (Visit 2; Week 0/Day 1) to confirm they continue to meet all inclusion/exclusion and are eligible for randomization. Note: The use of sponsor-supplied sterile eyelid wipes is to be discontinued after randomization at Visit 2. All subjects within this Cohort will be assessed for safety and exploratory efficacy. Both Investigator and subjects will be masked as to the IP. Subjects will be shown an instructional video on applying the investigational product to help ensure consistency in application across subjects. Further, the site should reinforce to the subject how to self-administer the IP to the eyelids and avoid ocular instillation. Subjects will self-administer a pre-specified volume (approximately 50 milligrams per eyelid) of 0.2% AXR-270 Cream or its Vehicle across the epidermis corresponding to the external surface overlying the tarsal plate of the upper and lower eyelids of both eyes. Refer to more detailed instructions in the Subject Dosing Instructions document. Blood draws for safety labs for all subjects will be performed prior to IP dosing in the clinic at Visit 2/Day 1. Following the in-clinic dose administration, subjects will be supplied with sufficient IP (2 tubes) to apply once daily at home in the evening during the treatment period. Subjects will self-administer IP QD in the evenings beginning on Day 2.

[figure not shown]
On the following week (Visit 3; Week 1/Day 8), the Investigators will examine the subject and perform all safety and efficacy assessments (excluding safety labs and dilated Ophthalmoscopy).

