Subjects will return for a Week 2 (Visit 4; Day 15) visit, wherein the Investigators will examine the subject and perform all safety and efficacy assessments (excluding safety labs and dilated Ophthalmoscopy). Subjects will return the used IP and will be instructed to use the 2nd IP tube dispensed at Visit 2 to apply once daily at home in the evening for the remaining 1 week of treatment duration.

Following the completion of the fifteenth (15th) subject from Visit 4 of Cohort 1, the Data Safety Review Committee (DSRC) will meet to review safety data and will make a recommendation about whether to escalate to the higher (2.0%) dose of AXR-270 Cream for Cohort 2, which if recommended, will begin immediately upon completion of enrollment in Cohort 1.

Subjects will return for a Week 3 (Visit 5; Day 22) visit, wherein the Investigators will examine the subject and perform all safety and efficacy assessments (including safety labs). Subjects should not dose at Visit 5/Day 22 and following the visit, subjects will exit the study. Remaining IP will be collected from every subject. (See Appendix 1 for procedures planned for this study).

FIGURE 1: STUDY SCHEMATIC (COHORT 1)

Note: Cohort 2 (AXR-270 2.0% Cream or vehicle) follows the same visit schedule as above and will start enrolling once enrollment of Cohort 1 is complete.

Cohort 2:

Following the completion of the fifteenth subject from Visit 4 of Cohort 1, the DSRC will meet to review safety data and will make a recommendation about whether to escalate to the

higher (2.0%) dose of AXR-270 Cream for Cohort 2, which if recommended, will begin immediately upon completion of enrollment in Cohort 1.

The Screening and study visits will be conducted in the same fashion as described above for Cohort 1. Approximately sixty-three (63) subjects will be randomized to 2.0% AXR-270 Cream or its Vehicle. A study schematic follows (Figure 1).

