- Determine if the subject is eligible to continue in the study. Do not continue screening any subject who does not meet eligibility requirements. Any subject who does not meet eligibility requirements will be designated as a Screen Failure.
- Instruct the subject to discontinue using all prohibited medications for the remainder of the study.
- If the subject is qualified, a four-week supply of commercial lid wipes will be provided.
- Schedule the subject to return for Visit 2 (Day 1) and remind subjects to bring the remaining lid wipes to Visit 2.

* May be performed at any time during the visit in order to facilitate subject and site schedules.

5.1.2. Visit 2 (Randomization): Day 1

Visit 2 will occur 14 (± 2 days) after Visit 1 (Screening). The following will be performed/assessed in both eyes:

- Evaluate continued eligibility
- Subject-rated symptom assessments (in this order):
 - Individual symptom assessment via VAS
 - OSDI
 - Modified BLISS
- Use of any concomitant medications since the last visit

- Occurrence of any AEs since the last visit
- BCVA
- Slit-lamp biomicroscopy and external eye exam
- TBUT
- FCS
- Investigator-rated assessment of signs of MGD
 - See Appendix 3. Assessment of Efficacy for full description of Investigator-rated assessments for objective signs of change from baseline
- LGS (at a subset of sites)
- Wait 15-20 minutes after LGS before proceeding
- Unanesthetized Schirmer test
- IOP
- Safety laboratory blood draw
- Determine if subject is eligible for randomization

For eligible subjects, the following is the process regarding administration of Double-Masked IP whereby the trained site staff will conduct the following procedures:

- Enter subject information into IWRS to determine randomization code and Kit Number. Cohort 1 versus Cohort 2 will be part of the Interactive Web Response System (IWRS) input
- Show the subjects an instructional video on applying the investigational product. Review Subject Dosing Instructions document, reiterating that the subject should administer IP across the entire surface (corresponding to the tarsal plate) of the upper and lower eyelids of both eyes
- Subject will self-administer first dose of double-masked IP in clinic under the supervision of site staff. The site staff will record the Day 1 dosing time in the source document.
- Assess for occurrence of any IP related AEs

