5.1.4. Visit 4: Day 15 (\pm 3 days)

This visit will occur on Day 15 as calculated from Visit 2: Day 1, and the following will be performed in both eyes:

- Subject-rated symptom assessments (in this order):
 - Individual Symptom Assessment via VAS
 - OSDI
 - Modified BLISS
- Use of any concomitant medications since the last visit
- Occurrence of any AEs since the last visit
- Review/collect Daily Dosing Diary #2 (including IP Comfort assessment) to assess compliance
- Collect used tube of double-masked IP and remind subject to begin dosing with second tube
- BCVA
- Slit-lamp biomicroscopy and external eye exam
- TBUT
- FCS
- Investigator-rated assessment of signs of MGD
 - See Appendix 3. Assessment of Efficacy for full description of Investigator-rated assessments for objective signs of change from baseline
- LGS (at a subset of sites)
- Wait 15-20 minutes after LGS before proceeding
- Unanesthetized Schirmer test
- IOP

- Reinforce the subject instructions to administer IP across the entire surface of the upper and lower eyelids of both eyes QD and to record each administration and IP comfort assessment on the daily dosing diary.
- Schedule the subject to return for Visit 5 (Day 22 \pm 3 days).
- **NOTE: For Cohort 1, when the first 15 subjects across all study sites have completed Visit 4, the DSRC will convene to review data and make recommendation regarding escalation to Cohort 2.**

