5.1.5. Visit 5: Day 22 (\pm 3 days)

This visit will occur on Day 22 as calculated from Visit 2: Day 1, and the following will be performed in both eyes:

- Subject-rated symptom assessments (in this order):
 - Individual Symptom Assessment via VAS
 - OSDI
 - Modified BLISS
- UPT (women of childbearing potential)
- Use of any concomitant medications since the last visit
- Occurrence of any AEs since the last visit
- Review/collect Daily Dosing Diary #3 (including IP Comfort assessment) to assess compliance
- BCVA
- Slit-lamp biomicroscopy and external eye exam
- TBUT
- FCS
- Investigator-rated assessment of signs of MGD
 - See Appendix 3. Assessment of Efficacy for full description of Investigator-rated assessments for objective signs of change from baseline
- LGS (at a subset of sites)
- Wait 15-20 minutes after LGS before proceeding
- Unanesthetized Schirmer test
- IOP
- Dilated Ophthalmoscopy
- Safety Laboratory blood draw

- Collect tube of double-masked IP and coolers/gel packs from the subject
- All subjects will be discharged from the study at this visit

5.1.6. **Unscheduled Visit**

Any visits or procedures performed beyond those specified within the protocol must be documented in the Unscheduled Visit pages of the electronic case report form (eCRF). Unscheduled visits may include but are not limited to reporting AEs, changes in concomitant medications, or ophthalmic assessments as deemed appropriate by an appropriately qualified physician.

5.1.7. **Early Termination Visit**

In the event of termination prior to Visit 5, every attempt will be made to ensure that all the following Visit 5 assessments are performed in both eyes at the Early Termination Visit prior to discharge from the study:

- Subject-rated symptom assessments (in this order):
 - Individual symptom assessments via VAS
 - OSDI
 - Modified BLISS
- Use of any concomitant medications since the last visit
- Occurrence of any AEs since the last visit
- Collect all used/unused IP and review/collect Daily Dosing Diaries (including IP Comfort assessment) to assess compliance
- UPT
- BCVA
- Slit-lamp biomicroscopy and external eye exam
- TBUT
- FCS
- Investigator-rated assessment of MGD
 - See Appendix 3. Assessment of Efficacy for full description of Investigator-rated assessments for objective signs of change from baseline
- LGS (at a subset of sites)

- Wait 15-20 minutes after LGS before proceeding
- Unanesthetized Schirmer test
- IOP measurement
- Dilated Ophthalmoscopy

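### The DSRC can recommend the tenfold step to 2.0% without being required to see any post-dose safety labs or dilated eye exams

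*Protocol*

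**What the plan says.** **Trigger.** Appendix 2 states: "A review of safety will be conducted by the DSRC after the last of those 15 subjects has completed Visit 4". The note in Protocol 5.1.4 agrees: "when the first 15 subjects across all study sites have completed Visit 4, the DSRC will convene to review data and make recommendation". One of the DSRC's three options is to expand to 2.0% on that review. The second option, a further look before deciding, is also set at two weeks: "conduct an additional review of safety information from the next 15 subjects reaching the 2-week mid-point of the study".

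**Start of Cohort 2.** Under Protocol 3.2 the higher dose, if recommended, "will begin immediately upon completion of enrollment in Cohort 1".

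**Safety labs.** Protocol 3.2: "Blood draws for safety labs for all subjects will be performed prior to IP dosing in the clinic at Visit 2/Day 1". At Visits 3 and 4 investigators "perform all safety and efficacy assessments (excluding safety labs and dilated Ophthalmoscopy"). The next scheduled draw is at Visit 5 (Protocol 5.1.5: "Safety Laboratory blood draw").

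**Dilated ophthalmoscopy.** Appendix 1 schedules it at Visit 1 and Visit 5 only. Protocol 5.1.7 asks for both assessments at an Early Termination Visit.

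**Charter.** Appendix 2 describes itself as a general plan and leaves procedures to a separate DSRC charter, which is not among the documents.

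**The concern.** Safety and tolerability are the primary objective (Protocol 2.1). The six safety endpoints in Protocol 3.1.1 include labs and dilated ophthalmoscopy. As written, the committee can recommend 2.0%, and Cohort 2 can begin dosing, without anyone being required to show it a single post-dose result on either.

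The step is tenfold. At about 50 mg per eyelid on four eyelids, the daily amount of cream is 200 mg, so the daily amount of drug rises from 0.4 mg (0.2%) to 4 mg (2.0%). Pharmacokinetics are not studied (SAP 2.5.2 and 4.7), so the labs are the only scheduled systemic laboratory measure. Cohort 2 follows the same schedule, and Appendix 2 sets no DSRC review within it. The Visit 5 results from Cohort 1 are therefore the only scheduled information from this trial on these two endpoints that could precede the higher dose.

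**Working it through.** **1. What is collected when (Protocol 3.2, 5.1 and Appendix 1)**

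| Assessment | Before first dose | Visit 3 | Visit 4 | Visit 5 |
|---|---|---|---|---|
| AEs, BCVA, slit lamp, IOP | yes | yes | yes | yes |
| Safety labs | Visit 2 | no | no | yes |
| Dilated ophthalmoscopy | Visit 1 | no | no | yes |

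The DSRC trigger falls at the fourth column and the missing data come in the fifth. The number of the 15 whose post-dose labs or dilated exam must be reviewed is 0.

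**2. Gap within one subject.** The windows are Day 12 to 18 for Visit 4 and Day 19 to 25 for Visit 5 (SAP 4.2.9, Table 2). The gap is 22 − 15 = 7 days nominally, with a minimum of 19 − 18 = 1 and a maximum of 25 − 12 = 13. For the 15th subject, scheduled Visit 5 results always come after the trigger.

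**3. How many of the 15 might be in hand anyway.** Visit 4 is a trigger and not a data cut-off, so earlier subjects may have reached Visit 5. The documents give no accrual rate, meeting lag or lab turnaround. Assume even accrual of r per week, nominal visit days, a lag of L weeks from trigger to meeting, and a turnaround of T weeks.

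- The meeting is at 14/r + 2 + L weeks after the first randomisation.
- Subject i has Visit 5 results at (i − 1)/r + 3 + T weeks.
- Results are in hand when i ≤ 15 − r(1 + T − L).

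| T (weeks) | L (weeks) | r = 3 | r = 5 | r = 10 | r = 15 |
|---|---|---|---|---|---|
| 0 | 0 | 12 | 10 | 5 | 0 |
| 0 | 0.5 | 13 | 12 | 10 | 7 |
| 0 | 1 | 15 | 15 | 15 | 15 |
| 1 | 0 | 9 | 5 | 0 | 0 |
| 1 | 1 | 12 | 10 | 5 | 0 |
| 1 | 2 | 15 | 15 | 15 | 15 |

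The T = 0 rows count subjects past nominal Visit 5. The T = 1 rows count lab results with a 7-day turnaround.

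**4. The option 2 review.** It is triggered at 29/r + 2 weeks, so with no lag results are in hand when i ≤ 30 − r(1 + T). All of the first 15 qualify if r ≤ 15 (T = 0) or r ≤ 15/2 = 7.5 (T = 1). The gap is smaller there, but that review is not required to include these data either.

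**5. Would waiting for the 15 delay Cohort 2?** The 63rd randomisation falls at 62/r weeks and the 15th subject's nominal Visit 5 at 14/r + 3 weeks. The slack is 48/r − 3 weeks. If that visit is on Day 25 (24 days after Day 1) and labs take 7 more days, 31 days replace the 3 weeks.

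| | r = 3 | r = 5 | r = 10 | r = 15 |
|---|---|---|---|---|
| Slack, nominal Day 22 (days) | 91 | 46.2 | 12.6 | 1.4 |
| Slack, Day 25 + 7 days (days) | 81 | 36.2 | 2.6 | −8.6 |

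Break-even accrual is 48/3 = 16 per week (nominal), 48/(24/7) = 14 (Day 25) and 48/(31/7) = 10.8 (Day 25 plus 7 days).

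**6. What the results could show.** With 2:1 allocation about 10 of the 15 receive 0.2%. For assumed true rates of 5%, 10% and 20%, the chance of at least one event among 10 is 1 − 0.95^10 = 40%, 1 − 0.90^10 = 65% and 1 − 0.80^10 = 89%. A finding that only these tests reveal cannot be seen until they are done.

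**The case against.** The facts and arithmetic are not in dispute. The case on the other side is about weight.

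- **The charter.** Which data the committee receives is normal charter content, and the charter may already require these results. This stands as a limit: the finding is about the protocol and SAP only.
- **Existing wording permits it.** The DSRC reviews safety data without a stated cut-off, so Visit 5 results in hand fall within scope. That is true, but permission leaves the amount seen to accrual and meeting date.
- **The practical gap may be small.** At 3 to 5 per week most of the 15 are past Visit 5 at the trigger, and with a one-week lag all are at every rate tabulated. This also stands. It shows that the data would usually exist, which makes requiring them cheap.
- **The named risks are covered.** The introduction names raised IOP, cataract and infection as corticosteroid risks to the eye. IOP, BCVA, slit lamp (lens, infiltrates, anterior chamber; Appendix 5) and AEs are collected at Visits 3 and 4. This stands and narrows the gap to systemic labs, retina and optic nerve head.
- **Earlier exposure.** Dermal cream was given for 42 days to 20 volunteers and for 21 days to 25 patients with atopic dermatitis, and doses were chosen on nonclinical safety multiples (Protocol 1 and 1.2). This helps, but the strengths of those creams are not given.
- **Other routes.** Investigators can withdraw a subject for a severe laboratory abnormality, SAEs reach the sponsor within 24 hours, and the sponsor can stop the trial. None of these returns Visit 5 results to the DSRC.

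**Conclusion.** The concern holds. The written rule allows a tenfold escalation with no post-dose labs or dilated exam reviewed, for two of six safety endpoints. Those two are not the ones that carry the main corticosteroid eye risks, so this is a change that should be made and not a fatal flaw. Confidence is medium. The absence of a requirement is plain in the protocol and SAP, but the charter is unseen, and the counts in hand rest on assumed accrual, meeting lag and turnaround. The defect is a missing requirement to look, more than a likely absence of data: the Visit 5 results of the first 15 would usually exist before the first 2.0% dose.

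**What to change.** Keep the Visit 4 review. Add to Appendix 2 and the charter that the Visit 5 (or Early Termination) safety labs and dilated ophthalmoscopy of the first 15 Cohort 1 subjects go to the DSRC, which confirms its recommendation before the first 2.0% dose. Under option 2, the DSRC sees those results together with the next 15 subjects' two-week data. The next 15 subjects' Visit 5 data need not be required: that would lower the break-even accrual to 33/3 = 11 per week (nominal), or 33/(31/7) = about 7.4 (Day 25 plus 7 days). If the charter already contains the requirement, one sentence in Appendix 2 makes it visible to sites and IRBs.

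**Cost.** A protocol amendment with IRB approval (Protocol 12.1) at 10 to 16 sites, a charter edit and a short DSRC confirmation. No new procedure, visit or subject.

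**Delay.** There is none below the break-even rates above, which are the same under option 2 because the added condition concerns the same 15 subjects. If Cohort 1 enrolment has already closed at the trigger, which takes about 24 per week or more (48/r ≤ 2 weeks), the wait is nominally 7 days (1 to 13). It is 14 days (8 to 20) with a 7-day turnaround. If Cohort 2 screening starts only after closure, the 14 (±2) day equalization period absorbs 12 to 16 days of this. The cohort is entered at randomisation ("Cohort 1 versus Cohort 2 will be part of the Interactive Web Response System (IWRS) input"), and the documents do not say whether subjects already in screening may roll over to Cohort 2. If they do, it absorbs none.
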